### 4) Physical and Laboratory Test Findings

- a) Screening laboratory values must meet the following criteria and should be obtained within 14 days prior to first dose:
  - i) Absolute neutrophil count  $\geq 1000/\mu\text{L}$  (no WBC growth factors for prior 14 days)
  - ii) Platelets  $\geq 50 \times 10^6/\text{mL}$  (no platelet transfusions for prior 14 days)
  - iii) Hemoglobin  $\geq 8.5 \text{ g/dL}$  (no RBC transfusions for prior 7 days)
  - iv) Creatinine clearance (CrCL)  $\geq 30 \text{ mL/min}$  (measured using the Cockcroft-Gault formula below):
$$\text{Female CrCL} = \frac{(140 - \text{age in years}) \times \text{weight in kg} \times 0.8}{72 \times \text{serum creatinine in mg/dL}}$$
$$\text{Male CrCL} = \frac{(140 - \text{age in years}) \times \text{weight in kg} \times 1.00}{72 \times \text{serum creatinine in mg/dL}}$$
- v) AST/ALT  $\leq 2.5 \times \text{ULN}$

- vi) Total bilirubin  $\leq 1.5 \times$  ULN (except participants with Gilbert Syndrome, who can have total bilirubin  $< 3.0$  mg/dL)
- b) Participants require left ventricular ejection fraction over 50% at rest. (Changed per Administrative Letter 02, 21-Aug-2019).
- c) Pulmonary Function Test with diffusing capacity of the lung for carbon monoxide (DLCO)  $\geq 60\%$  (hemoglobin-adjusted)

## 6.2 Exclusion Criteria

### 1) Target Disease Exceptions

- a) Known central nervous system lymphoma.
- b) Participants with nodular lymphocyte-predominant HL.

### 2) Medical History and Concurrent Diseases

- a) Participants with known history of pancreatitis or progressive multifocal leukoencephalopathy (PML)
- b) Participants with active interstitial pneumonitis or CT evidence of  $\geq$  Grade 1 pneumonitis.
  - i) If the participant has a history of interstitial pneumonitis, they must have CT evidence of resolution.
- c) Participants with neuropathy  $\geq$  Grade 2, infection  $\geq$  Grade 3, or documented history of coronary artery disease, cardiovascular accidents, or congestive heart failure (CHF) class III/IV.
- d) Any serious or uncontrolled medical disorder that, in the opinion of the investigator, may increase the risk associated with study participation or study treatment administration, impair the ability of the participant to receive protocol therapy, or interfere with the interpretation of study results
- e) Prior malignancies (other than HL) are excluded unless a complete remission was achieved at least 3 years prior to study entry and no additional therapy is required or anticipated to be required during the study period (exceptions include, but are not limited to, non-melanoma skin cancers; in situ bladder cancer, in situ gastric cancer, or in situ colon cancers; in situ cervical cancers/dysplasia; in situ carcinoma of the prostate; or breast carcinoma in situ).
- f) Participants with an active, known or suspected autoimmune disease. Participants with type I diabetes mellitus, hypothyroidism only requiring hormone replacement, skin disorders (such as vitiligo, psoriasis, or alopecia) not requiring systemic treatment, or conditions not expected to recur in the absence of an external trigger are permitted to enroll. For any cases of uncertainty, it is recommended that a BMS medical monitor be consulted prior to signing informed consent.
- g) Participants with a condition requiring systemic treatment with either corticosteroids ( $> 10$  mg daily prednisone equivalents) or other immunosuppressive medications within 14 days of study treatment administration. Inhaled or topical steroids, and adrenal replacement doses 10mg daily are permitted in the absence of active autoimmune disease.
- h) Evidence of active brain metastases on brain imaging (ie, MRI or contrast CT).

### 3) Prior/Concomitant Therapy

- a) ASCT  $\leq$  30 days prior to first dose of study treatment
- b) Prior chemotherapy within 4 weeks, nitrosureas within 6 weeks, therapeutic anticancer antibodies within 4 weeks, radio- or toxin or major surgery within 2 weeks prior to first dose of study treatment.
- c) Carmustine (BCNU)  $\geq$  600mg/m^2 received as part of the pre-transplant conditioning regimen.
- d) Prior radiation therapy within 3 weeks, or chest radiation  $\leq$  24 weeks prior to first dose of the study treatment.
- e) Prior treatment with an anti-PD-1, anti-PD-L1, anti-PD-L2, anti-CD137, or anti-CTLA-4 antibody (including ipilimumab or any other antibody or drug specifically targeting T-cell co-stimulation or checkpoint pathways.
- f) Prior allogeneic transplant
- g) BV refractory patients as identified by a failure to achieve a PR or CR, relapse, or progression within 3 months of receiving BV treatment (BV treatment as defined by: patients who previously received BV as a single agent or in combination with chemotherapy in any line of treatment [eg, induction, salvage, or consolidation post-ASCT]).

### 4) Physical and Laboratory Test Findings

- a) Any positive test result for hepatitis B virus or hepatitis C virus indicating presence of virus, eg, Hepatitis B surface antigen (HBsAg, Australia antigen) positive, or Hepatitis C antibody (anti-HCV) positive (except if HCV-RNA negative)
- b) Known history of testing positive for human immunodeficiency virus (HIV) or known acquired immunodeficiency syndrome (AIDS).
  - i) Testing for HIV must be performed at sites where mandated locally

### 5) Allergies and Adverse Drug Reaction

- a) History of allergy to drug components

History of severe hypersensitivity reaction  $\geq$  Grade 3 to any monoclonal antibody with the following exception: participants who experienced Grade 3 or 4 infusion-related reaction with the first dose of rituximab, but who were able to receive subsequent rituximab without recurrence of Grade 3 or 4 infusion-related reaction are eligible.

### 6) Other Exclusion Criteria

- a) Prisoners or participants who are involuntarily incarcerated. (Note: under certain specific circumstances, a person who has been imprisoned may be included or permitted to continue as a participant. Strict conditions apply and Bristol-Myers Squibb [BMS] approval is required).
- b) Participants who are compulsorily detained for treatment of either a psychiatric or physical (eg, infectious disease) illness.
- c) Females who are pregnant or breastfeeding

Eligibility criteria for this study have been carefully considered to ensure the safety of the study participants and that the results of the study can be used. It is imperative that participants fully meet all eligibility criteria.

### **6.3 Lifestyle Restrictions**

Not applicable. No restrictions are required.

### **6.4 Screen Failures**

Screen failures are defined as participants who consent to participate in the clinical study but are not subsequently randomized. A minimal set of screen failure information is required to ensure transparent reporting of screen failure participants, to meet the Consolidated Standards of Reporting Trials (CONSORT) publishing requirements, and to respond to queries from regulatory authorities. Minimal information includes date of consent, demography, screen failure details, eligibility criteria, and any serious AEs.

#### **6.4.1 Retesting During Screening or Lead-In Period**

**Participant Re-enrollment:** This study permits the re-enrollment of a participant that has discontinued the study as a pre-treatment failure (ie, participant has not been randomized / has not been treated). If re-enrolled, the participant must be re-consented.

Retesting of laboratory parameters and/or other assessments within any single Screening or Lead-in period will be permitted (in addition to any parameters that require a confirmatory value).

The most current result prior to Enrollment and Randomization (randomized arms) is the value by which study inclusion will be assessed, as it represents the participant's most current clinical state.

Laboratory parameters and/or assessments that are included in the Screening Procedural Outline, [Table 2-1](#), may be repeated in an effort to find all possible well-qualified participants. Consultation with the Medical Monitor may be needed to identify whether repeat testing of any particular parameter is clinically relevant.

Enrollment in this study was stopped on 17-Oct-2019 at the decision of the Sponsor.

## **7 TREATMENT**

Study treatment is defined as any investigational treatment(s), marketed product(s), placebo or medical device intended to be administered to a study participant according to the study enrollment and randomization.

Study treatment includes 2 Investigational [Medicinal] Products (IPs/IMPs) ([Table 7-1](#)). In this study, the IPs/IMPs are nivolumab and BV.

An investigational product, also known as investigational medicinal product in some regions, is defined a pharmaceutical form of an active substance or placebo being tested or used as a reference in a clinical study, including products already with a marketing authorization but used or assembled (formulated or packaged) differently than the authorized form, or used for an unauthorized indication, or when used to gain further information about the authorized form.

Infusion-related supplies (eg, IV bags, in-line filters, 0.9% sodium chloride injection) will not be supplied by the sponsor and should be purchased locally if permitted by local regulations.

Please refer to the current version of the IB and/or pharmacy manual for complete storage, handling, dispensing, and infusion information for nivolumab. See also the Nivolumab IB (Section 3 of the IB) or prescribing information (eg, USPI [Section 11], SmPC [EMA version, Sections 1, 2, 3 of the SmPC]), or country-specific product label for more information.

For the constituents of brentuximab vedotin (BV) see the current version of the associated product labels and SmPCs (respectively footnoted) for more information.

Premedications or medications used to treat infusion-related reactions should be sourced by the investigative sites if available and permitted by local regulations.

**Table 7-1: Study treatments for CA209812**

Product Description / Class and Dosage Form	Potency	IP/ Non-IMP	Blinded or Open Label	Packaging / Appearance	Storage Conditions (per label)
Nivolumab (BMS-936558-01) Solution for Injection	100 mg (10 mg/mL)	IP	Open Label	Clear to opalescent colorless to pale yellow liquid. May contain particles. Carton contains 5 vials of 100mg	2° to 8°C. Protect from light and freezing
Brentuximab Vedotin Powder for Solution for Injection a	50 mg	IP	Open-label	White to off-white lyophilized preservative-free cake or powder in a single-use vial for reconstitution	2° to 8°C. Protect from light and freezing

a May be obtained by the investigational sites in certain countries as local commercial product (which may be available as a different potency/package size than listed above) if local regulations allow. Locally sourced marketed product utilized for this study should be prepared and stored in accordance with the package insert, summary of product characteristics (SmPC), or equivalent document.

## 7.1 Treatments Administered

Infusions will be performed over a period of once every 3 weeks. Participants should begin study treatment within 3 calendar days of randomization. Participants will be monitored continuously for AEs while on study. Study treatment modifications (eg, dose delay or discontinuation) will be based on specific laboratory and AE criteria (Section 7.4). Doses of study treatment may be interrupted, withheld, or discontinued depending on how well the participant tolerates the study treatment. Treatment with nivolumab will be continued as described in Section 5.1 until disease progression or unacceptable toxicity. Participants treated with nivolumab who achieve a CR may discontinue treatment after a maximum of 2 years of therapy, provided that there is no prohibitive toxicity. Administration of BV should be discontinued after a maximum of 16 cycles, or until disease progression or unacceptable toxicity, whichever occurs first.

All participants who discontinue therapy will be followed through Safety Follow-up Visit 2.

### **Nivolumab and Brentuximab vedotin arm**

Participants should receive nivolumab at a dose of 360 mg as a 30-minute infusion on Day 1 of each treatment cycle until progression, unacceptable toxicity, withdrawal of consent, or the study ends, whichever occurs first. No dose escalations or reductions of nivolumab are allowed. Premedications are not recommended for the first dose of nivolumab. For 30-minute infusions, infusion durations are  $\pm 5$  minutes. For Q3W dosing cycles, participants may be dosed within a  $\pm 3$  day window.

For participants in the nivolumab/BV arm, BV will be administered first as a 30-minute infusion followed by a minimum 30-minute rest prior to the nivolumab infusion. Brentuximab vedotin will be administered as a 1.8 mg/kg dose on Day 1 of each treatment cycle every 3 weeks for 16 cycles. In the absence of infusion-related reactions, the infusion rate for all participants should be calculated in order to achieve a 30-minute infusion period. Brentuximab vedotin must not be administered as an IV push or bolus nor mixed with other medications. Dosing of BV is based on participant's actual body weight. Doses must be adjusted for participants who experience a  $\geq 10\%$  change in weight from baseline. Other dose adjustments for changes in body weight are permitted per institutional standard. An exception to weight-based dosing is made for participants weighing greater than 100 kg; doses will be based on 100 kg for these individuals. Rounding is permissible within 5% of the nominal dose.

Nivolumab Injection, 100 mg/10 mL (10 mg/mL) is to be administered as an IV infusion through a 0.2-micron to 1.2-micron pore size, low-protein binding in-line filter at the protocol-specified doses. It is not to be administered as an IV push or bolus injection. Nivolumab injection can be infused undiluted (10 mg/mL) or diluted with 0.9% Sodium Chloride Injection, USP or 5% Dextrose Injection, USP to protein concentrations as low as 1 mg/mL. Instructions for dilution and infusion of nivolumab injection may be provided in the clinical protocol, pharmacy binder, or pharmacy reference sheet. Care must be taken to assure sterility of the prepared solution as the product does not contain any antimicrobial preservative or bacteriostatic agent.

Nivolumab infusions are compatible with polyvinyl chloride (PVC) or polyolefin containers and infusion sets, and glass bottles.

Participants may continue on nivolumab or BV alone if required to discontinue one of the study medications. It is recommended to consult with the medical monitor before discontinuing one of the study medications.

Participants should be carefully monitored for infusion reactions during study treatment administration. If an acute infusion reaction related to nivolumab is noted, participants should be managed according to [Section 7.1.5](#).

### **Brentuximab Vedotin arm**

Brentuximab Vedotin will be administered as a 1.8 mg/kg dose on Day 1 of each treatment cycle every 3 weeks for 16 cycles as a 30-minute infusion. In the absence of infusion-related reactions, the infusion rate for all participants should be calculated in order to achieve a 30-minute infusion period. Brentuximab vedotin must not be administered as an IV push or bolus nor mixed with other medications. Dosing of BV is based on participant's actual body weight. Doses must be adjusted for participants who experience a  $\geq 10\%$  change in weight from baseline. Other dose adjustments for changes in body weight are permitted per institutional standard. An exception to weight-based dosing is made for participants weighing greater than 100 kg; doses will be based on 100 kg for these individuals. Rounding is permissible within 5% of the nominal dose.

### **7.1.2 Criteria to Resume Study treatment (Nivolumab)**

Participants may resume study treatment with study treatment when the study treatment-related AE(s) resolve to Grade  $\leq$  1 or baseline value, with the following exceptions:

- Participants may resume study treatment in the presence of Grade 2 fatigue
- Participants who have not experienced a Grade 3 study treatment-related skin AE may resume study treatment in the presence of Grade 2 skin toxicity
- Participants with combined Grade 2 AST/ALT AND total bilirubin values meeting discontinuation parameters ([Section 7.1.6](#)) should have study treatment permanently discontinued
- Study treatment-related pulmonary toxicity, diarrhea, colitis, uveitis or neurological toxicity, must have resolved to baseline before study treatment is resumed. Participants with persistent Grade 1 pneumonitis after completion of a steroid taper over at least 1 month may be eligible for retreatment if discussed with and approved by BMS Medical Monitor
- Participants with drug-related endocrinopathies adequately controlled with only physiologic hormone replacement may resume treatment after consultation with the BMS Medical Monitor. Adrenal insufficiency requires discontinuation regardless of control with hormone replacement
- For participants with Grade 2 AST, ALT and/or Total Bilirubin Abnormalities, dosing may resume when laboratory values return to baseline and management with corticosteroids, if needed, is complete

If the criteria to resume study treatment are met, the participant should restart study treatment at the next scheduled timepoint per protocol. However, if the study treatment is withheld past the window period of the next scheduled timepoint per protocol to ensure adequate recovery from the adverse event or tapering of immunosuppression, the dosing should continue to be withheld until the subsequent scheduled timepoint.

#### **7.1.4 Management Algorithms for Immuno-Oncology Agents**

Immuno-oncology (I-O) agents are associated with AEs that can differ in severity and duration than AEs caused by other therapeutic classes. Nivolumab is considered an I-O agent in this protocol. Early recognition and management of AEs associated with I-O agents may mitigate severe toxicity. Management Algorithms have been developed to assist investigators in assessing and managing the following groups of AEs:

- Gastrointestinal
- Renal
- Pulmonary
- Hepatic
- Endocrinopathy
- Skin
- Neurological
- Myocarditis

The above algorithms are found in the IB and [Appendix 5](#) of this protocol.

#### **7.1.5 Treatment of Infusion-related Reactions (Nivolumab/Brentuximab Vedotin)**

Infusion-related reactions may occur during the infusion of study treatment(s). The infusion should be administered at a site properly equipped and staffed to manage anaphylaxis should it occur. All supportive measures consistent with optimal patient care should be given throughout the study according to institutional standards. Supportive measures may include extending the infusion time and/or administering medications for infusion-related reactions.

Infusion or hypersensitivity reactions may occur to either brentuximab vedotin or nivolumab. If such a reaction were to occur, it might manifest with fever, chills, rigors, headache, rash, pruritus, arthralgias, hypotension, hypertension, bronchospasm, or other allergic-like reactions. Infusion reactions should be graded according to NCI CTCAE (Version 4.03) guidelines. All Grade 3 or 4 infusion reactions should be reported within 24 hours to the study medical monitor and reported as an SAE if it meets the criteria. Infusion reactions should be graded according to National Cancer Institute Common Technology Criteria for Adverse Events (NCI CTCAE, Version 4.03) guidelines.

Subjects who experience a Grade 1 or Grade 2 infusion-related reaction should be premedicated for subsequent infusions. Premedication should be given at least 30 minutes prior to dosing study drug(s) and should include an antihistamine and corticosteroid. Recommended doses are: diphenhydramine 25 to 50 mg IV (or equivalent) and methylprednisolone 40 mg IV (or equivalent). In addition, acetaminophen/paracetamol 325 to 1000 mg and ranitidine 50 mg IV may be given. If the onset of a reaction occurs during an infusion, the infusion may be interrupted for treatment of the infusion-related reaction, including treatment with antihistamines, corticosteroids, and/or bronchodilator therapy, as appropriate. Subjects who experience a Grade 3 infusion-related reaction to brentuximab vedotin or nivolumab may potentially receive additional

treatment with the study drug(s) at the discretion of the investigator after discussion with the sponsor.

If anaphylaxis or a Grade 4 infusion-related reaction occurs, administration of the implicated agent(s) (brentuximab vedotin and/or nivolumab) should be immediately and permanently discontinued. The investigator should begin an IV infusion of normal saline and treat the participant as follows: Recommend bronchodilators, epinephrine 0.2 to 1 mg of a 1:1000 solution for subcutaneous administration or 0.1 to 0.25 mg of a 1:10,000 solution injected slowly for IV administration, and/or diphenhydramine 50 mg IV with methylprednisolone 100 mg IV (or equivalent), as needed. Participant should be monitored until the investigator is comfortable that the symptoms will not recur.

In case of late-occurring hypersensitivity symptoms to nivolumab (eg, appearance of a localized or generalized pruritus within 1 week after nivolumab treatment), symptomatic treatment may be given (eg, oral antihistamine or corticosteroids).

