### **7.1.6 Dose Discontinuation Criteria (Nivolumab)**

Nivolumab treatment should be permanently discontinued for the following:

- Any Grade 2 study treatment-related uveitis or eye pain or blurred vision that does not respond to topical therapy and does not improve to Grade 1 severity within the re-treatment period OR requires systemic treatment
- Any Grade 3 non-skin, study treatment-related AE lasting > 7 days or recurs, with the following exceptions for laboratory abnormalities, study treatment-related uveitis, pneumonitis, bronchospasm, hypersensitivity reactions, infusion reactions, and endocrinopathies:
  - Grade 3 study treatment-related uveitis, pneumonitis, bronchospasm, neurologic toxicity, myocarditis, hypersensitivity reaction, or infusion reaction of any duration require discontinuation
  - Grade 3 study treatment-related endocrinopathies adequately controlled with only physiologic hormone replacement do not require discontinuation. Adrenal insufficiency requires discontinuation regardless of control with hormone replacement.
  - Grade 3 study treatment-related laboratory abnormalities do not require treatment discontinuation except:
    - Grade 3 study treatment-related thrombocytopenia > 7 days or associated with clinically significant bleeding requires discontinuation\*
    - AST or ALT > 8 x ULN or Total Bilirubin > 5 x ULN requires discontinuation
    - Concurrent AST or ALT > 3 x ULN and Total Bilirubin > 2 x ULN

\* In most cases of Grade 3 AST or ALT elevation, study treatment(s) will be permanently discontinued. If the investigator determines a possible favorable benefit/risk ratio that warrants continuation of study treatment(s), a discussion between the investigator and the BMS Medical Monitor/designee must occur.

- Any Grade 4 study treatment-related adverse event or laboratory abnormality (including but not limited to creatinine, AST, ALT, or TBili), except for the following events which do not require discontinuation
  - Grade 4 neutropenia  $\leq 7$  days
  - Grade 4 lymphopenia or leukopenia
  - Isolated Grade 4 amylase or lipase abnormalities that are not associated with symptoms or clinical manifestations of pancreatitis. Consult Medical Monitor for Grade 4 amylase and lipase abnormalities
  - Isolated Grade 4 electrolyte imbalances/abnormalities that are not associated with clinical sequelae and are corrected with supplementation/appropriate management within 72 hours of their onset

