### **7.4.2 Brentuximab vedotin**

The recommended dose modifications for BV treatment associated toxicity are provided in [Table 7.4.2-1](#). Doses reduced for BV-related toxicity should not be re-escalated without discussion with the sponsor. Dose escalation of BV beyond 1.8 mg/kg is not permitted. Dose reductions below 1.2 mg/kg are not allowed.

If BV treatment is delayed for any reason, other treatments must be continued. Participants who require delay of BV should be re-evaluated frequently and BV dosing resumed when re-treatment criteria are met. Dose delays of more than 3 weeks may be allowed after discussion with the study medical monitor.

Recommendations for management of infusion related reactions due to BV are described in [Section 7.1.5](#).

Participants who discontinue nivolumab treatment due to a treatment-related AE may continue treatment with BV for a maximum of 16 cycles, or until disease progression or unacceptable toxicity, whichever occurs first. Participants who discontinue BV due to a treatment-related AE may continue to receive nivolumab treatment until disease progression or unacceptable toxicity.

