**Table 7.4.2-1: Dose Modifications for Brentuximab Vedotin**

Toxicity	Grade 1	Grade 2	Grade 3	Grade 4
Peripheral Neuropathy	Continue at same dose level	Hold until peripheral neuropathy resolves to $\leq$ Grade 1 and then resume treatment at 1.2 mg/kg a	Withhold (delay) until toxicity resolves to $\leq$ Grade 2 or baseline, then resume treatment at 1.2 mg/kg or discontinue if reduction has already occurred.	Discontinue treatment
Non-hematologic (except peripheral neuropathy)	Continue at same dose level	Continue at same dose level	Withhold (delay) dose until toxicity is $\leq$ Grade 2 or has returned to baseline, then resume treatment at the same dose level b	Withhold dose until toxicity is $\leq$ Grade 2 or has returned to baseline, then reduce dose to 1.2 mg/kg and resume treatment, or discontinue at the discretion of the investigator a,b,c
Hematologic d	Continue at same dose level	Continue at same dose level	Withhold (delay) until toxicity resolves to $\leq$ Grade 2 or baseline, then resume treatment at the same dose level. c Growth factor support (G-CSF or GM-CSF) should be considered for subsequent cycles. If Grade 4 neutropenia recurs despite growth factor support, consider discontinuation.	Discontinue treatment

a Dose reductions below 1.2 mg/kg are not allowed, and toxicities should be managed with dose delays

b Participants who develop Grade 3 or 4 electrolyte laboratory abnormalities may continue study treatment without dose delay

c Treatment should be discontinued for participants who experience Grade 4 infusion-related reactions.

d Support with blood product transfusions allowed per institutional standard of care.

e Participants who develop Grade 3 or 4 lymphopenia may continue study treatment without dose delay.

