## **8 DISCONTINUATION CRITERIA**

### **8.1 Discontinuation from Study Treatment**

Participants **MUST** discontinue the investigational product(s) for any of the following reasons:

- Disease progression as determined by investigator assessment following the guidelines given in [Appendix 6](#)
- Participant's request to stop study treatment. Participants who request to discontinue study treatment will remain in the study and must continue to be followed for protocol specified follow-up procedures. The only exception to this is when a participant specifically withdraws consent for any further contact with him/her or persons previously authorized by participant to provide this information
- Any clinical adverse event (AE), laboratory abnormality or intercurrent illness which, in the opinion of the investigator, indicates that continued participation in the study is not in the best interest of the participant
- Termination of the study by Bristol-Myers Squibb (BMS)
- Loss of ability to freely provide consent through imprisonment or involuntarily incarceration for treatment of either a psychiatric or physical (eg, infectious disease) illness
- Additional protocol specified reasons for discontinuation.

Refer to the Schedule of Activities for data to be collected at the time of treatment discontinuation and follow-up and for any further evaluations that can be completed.

In the case of pregnancy, the investigator must immediately notify the BMS Medical Monitor/designee of this event. In the event a normal healthy female participant becomes pregnant during a clinical trial, the study treatment must be discontinued immediately. In most cases, the study treatment will be permanently discontinued in an appropriate manner (eg, dose tapering if necessary for participant safety). Please call the BMS Medical Monitor within 24 hours of awareness of the pregnancy. If the investigator determines a possible favorable benefit/risk ratio that warrants continuation of study treatment, a discussion between the investigator and the BMS Medical Monitor/designee must occur.

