## 9 STUDY ASSESSMENTS AND PROCEDURES

- Study procedures and timing are summarized in the Schedule of Activities.
- Protocol waivers or exemptions are not allowed.
- All immediate safety concerns must be discussed with the Sponsor immediately upon occurrence or awareness to determine if the participant should continue or discontinue treatment.
- Adherence to the study design requirements, including those specified in the Schedule of Activities, is essential and required for study conduct.
- All screening evaluations must be completed and reviewed to confirm that potential participants meet all eligibility criteria before randomization. The investigator will maintain a screening log to record details of all participants screened and to confirm eligibility or record reasons for screening failure, as applicable.
- Procedures conducted as part of the participant's routine clinical management (eg, blood count) and obtained before signing of informed consent may be utilized for screening or baseline purposes provided the procedure meets the protocol-defined criteria and has been performed within the timeframe defined in the Schedule of Activities.

Additional measures, including non-study required laboratory tests, should be performed as clinically indicated or to comply with local regulations. Laboratory toxicities (eg, suspected drug induced liver enzyme evaluations) will be monitored during the follow-up phase via on site/local labs until all study drug related toxicities resolve, return to baseline, or are deemed irreversible.

If a participant shows pulmonary-related signs (hypoxia, fever) or symptoms (eg, dyspnea, cough, fever) consistent with possible pulmonary adverse events, the participant should be immediately evaluated to rule out pulmonary toxicity, according to the suspected pulmonary toxicity management algorithm in the BMS-936558 (nivolumab) Investigator Brochure.

Some of the assessments referred to in this section may not be captured as data in the eCRF. They are intended to be used as safety monitoring by the treating physician. Additional testing or assessments may be performed as clinically necessary or where required by institutional or local regulations.

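### After a Grade 3 infusion reaction to nivolumab, Protocol Section 7.1.5 leaves re-treatment open while Section 7.1.6 requires permanent discontinuation

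*Protocol*

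**What the plan says.** Section 7.1.5 covers infusion reactions to both drugs. For Grade 3 it states: "Subjects who experience a Grade 3 infusion-related reaction to brentuximab vedotin or nivolumab may potentially receive additional" treatment, subject to the investigator's judgement and a prior discussion with the sponsor. Its only mandatory permanent stop is for anaphylaxis or a Grade 4 reaction, and that stop applies to whichever agent is implicated.

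Section 7.1.6 lists the events for which nivolumab is to be stopped for good. Among treatment-related Grade 3 events it names several that are stricter than the general rule of more than 7 days or recurrence, ending with: "hypersensitivity reaction, or infusion reaction of any duration require discontinuation".

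Four other places bear on the point:

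- Section 7.1, combination arm: "If an acute infusion reaction related to nivolumab is noted, participants should be managed according to" Section 7.1.5.
- Table 7.4.2-1, footnote c, for BV: "Treatment should be discontinued for participants who experience Grade 4 infusion-related reactions".
- Section 7.4.2: "Participants who discontinue nivolumab treatment due to a treatment-related AE may continue treatment with BV", within the usual limits of 16 cycles, progression or toxicity.
- Section 8.1 makes stopping mandatory for a list of reasons that ends with "Additional protocol specified reasons for discontinuation".

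**The concern.** A participant with a Grade 3 infusion reaction to nivolumab falls under both sections. One leaves a further dose open; the other forbids it. Both are current protocol text, not entries in the amendment log.

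What is at stake is re-exposure after a severe reaction. Enrollment has closed, but enrolled participants with clinical benefit may stay on treatment, and nivolumab has no fixed number of cycles. A site that follows the cross-reference in Section 7.1 reaches the permissive rule and could propose a re-challenge that the stopping rule excludes. Two sites, or two sponsor monitors, could handle the same event differently and each point to protocol text.

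**Working it through.** There is no figure to reproduce, so the check sets the rules side by side.

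| Event | Section 7.1.5 | Drug-specific rule | Agree? |
|---|---|---|---|
| Grade 3 reaction to BV | Further drug possible after sponsor discussion | Section 7.1.7 points to Table 7.4.2-1: withhold for Grade 3 non-hematologic toxicity, then resume at the same dose | Yes |
| Grade 4 reaction to BV | Permanent stop | Table 7.4.2-1, footnote c: stop | Yes |
| Grade 3 reaction to nivolumab | Further drug possible after sponsor discussion | Section 7.1.6: permanent stop, whatever the duration | **No** |
| Grade 4 reaction to nivolumab | Permanent stop | Section 7.1.6: Grade 4 treatment-related events stop nivolumab, and infusion reactions are not among the exceptions | Yes |

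Only one cell conflicts. Three ways of reconciling it were tried.

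1. *The drug that may be given again in 7.1.5 is only the other one.* The text does not say this. The next paragraph of 7.1.5 does single out the implicated agent, but only for Grade 4 and anaphylaxis. The natural reading of that contrast is that the implicated drug may be given again after Grade 3.
2. *Section 7.1.6 contains an implied override.* It writes its overrides out where they are meant: a benefit-risk discussion for Grade 3 AST or ALT elevation, and medical monitor involvement for Grade 4 endocrinopathies and for dose holds beyond 6 weeks. Infusion reactions have none.
3. *Section 7.1.5 is the specific exception to 7.1.6.* Section 7.1.6 itself picks out infusion reactions as a special case and makes the rule stricter for them. It does not refer back to 7.1.5.

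Two things suggest that the stricter rule is the intended one. The summary of changes shows that Revised Protocol 01 edited this same list, adding neurologic toxicity and myocarditis, and infusion reaction is still in it. Section 6.2 excludes people with a past severe (Grade 3 or higher) hypersensitivity reaction to any monoclonal antibody, with one narrow rituximab exception, which sits poorly with open-ended re-challenge on study.

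*Size.* Section 10 gives 23 randomized, planned 1:1. An even split puts 11 or 12 in the nivolumab arm. The actual split and the block size are not given. With 4 strata and permuted blocks, the largest possible imbalance is 3 for an assumed block size of 2 (split 10:13), 7 for size 4 (8:15) and 11 for size 6 (6:17). These ranges bound the arm size only. How many are still on nivolumab is not stated. The infusion and hypersensitivity reaction rates in Section 5.5.4 come from another study and were all Grade 1 or 2, so they give no Grade 3 rate.

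**The case against.** The strongest reply has four parts.

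- *The risk is already gated.* Section 7.1.5 grants nothing automatically: Grade 3 and 4 reactions go to the medical monitor within 24 hours, and any re-treatment needs a discussion with the sponsor, who also wrote 7.1.6. This stands, and it limits the severity. It does not remove the contradiction, because the monitor faces the same two rules.
- *Section 7.1.6 may reach further than nivolumab.* It speaks of reactions related to study treatment, which Section 7 defines to include BV. Read literally, a Grade 3 reaction to BV would also stop nivolumab, and limiting 7.1.5 to BV would not cure that. Section 7.1.1 largely answers this, since it lets nivolumab continue when the toxicity is due to BV. A clarifying word in 7.1.6 would still help.
- *The narrower reading of 7.1.5 is not strictly excluded.* The protocol repeatedly lets one drug continue while the other is held or stopped. That is fair, but a rule on re-exposure should not depend on the less natural reading.
- *Some supporting text is weaker than it looks.* Section 7.1's cross-reference concerns managing the acute reaction and does not tell sites to ignore 7.1.6. The sentence in Section 9, "Protocol waivers or exemptions are not allowed", does not settle which section controls, since a site following 7.1.5 is also following the protocol. Both points are accepted. The mandatory stop in Section 8.1 is the better support for 7.1.6, and the conflict does not depend on the Section 9 sentence.

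**Conclusion.** The concern holds. For a Grade 3 infusion reaction to nivolumab the protocol gives two incompatible instructions, and no other passage reconciles them. The BV rules are consistent. Section 7.1.6, read with Section 8.1, is the better candidate for the controlling rule, so the Grade 3 sentence in 7.1.5 is wrong as written so far as it covers nivolumab.

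It should be fixed, though the practical risk is limited: one arm of a 23-participant trial with enrollment closed, a sponsor gate before any re-dosing, and probably few Grade 3 reactions, a number the documents do not allow anyone to estimate. The consequence is for participant safety and consistent conduct across sites. No efficacy estimate, error rate or other statistical figure is affected. The conclusion rests on reading the drug that may be given again in 7.1.5 as including the one that caused the reaction.

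**What to change.** Limit the Grade 3 sentence in Section 7.1.5 to brentuximab vedotin, and add: *A Grade 3 infusion-related reaction to nivolumab requires permanent discontinuation of nivolumab (Section 7.1.6); BV may continue.* Section 7.4.2 already allows BV to go on. It would be tidy to state in 7.1.6 at the same time that the stop is triggered by a reaction attributed to nivolumab, in line with Section 7.1.1.

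If the sponsor's clinical team does want to allow nivolumab re-challenge after Grade 3, the exception and its conditions should be written into 7.1.6 instead. Either way, one rule has to be chosen.

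The cost is a sentence of text and an administrative letter, with sites informing their IRB/IEC as Appendix 2 requires. The Document History shows that an administrative letter has already been used in this trial to correct inconsistencies. No new data collection or analysis is needed.
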